A Multidisciplinary Approach to the Treatment of Encopresis in Children with Autism Spectrum Disorders

Department of Defense Study

PI: [name].

Assistant Professor of Pediatrics - Division of Autism and Related Disorders

Marcus Autism Center

NCT Number: NCT03197922

Protocol Version 4.3

Protocol date: August 24, 2021

History of Protocol Changes

Version 4.3 08/24/2021

- **Added REDCap as a data collection tool for collecting consent signature and parent measures.**

Version 4.2 06/15/2020

- **Added in the ADI-R and CARS-2 assessments as additional ASD diagnostic tools**
- **Added in the option to do the medical assessment through telehealth, specifically zoom**

Version 4.1 03/18/2020

- **Added language to include that TAU and MIE appointments can be through Telehealth**
- **Corrected total enrollment number to 138 instead of 112 because 112 did not include the participants that were previously enrolled into the MIE 1 week group**

Version 4.0 10/15/2019

- **Removed MIE 1 week group**
- **Corrected visit window and continence language**

Version 3.9 05/30/2019

- **Corrected title of protocol**
- **Changed IRB notification of “would” to “may” for cases of problem behavior.**
- **Removed language about participants being enrolled in IRB #53959.**
- **Included information on holds/restraining for participants engaging in problem behavior**

Version 3.8 01/24/2019

- **We changed the definition of “urine continent” under our inclusion criteria. It will now be “Over half of the voids are continent when the child is with the parent and when the child is on a typical toileting routine.**
- **We removed number 6 under inclusion criteria because in our last amendment we said subject would no longer be enrolled in our IRB# 53959**
- **We removed the section on the top of page 22 that says, “Also, subjects will be enrolled in IRB 53959 (MAC), which permits and facilitates the collection of their data. If the subject does not agree to be in IRB 53959, they will be excluded”**
- **Version 3.7 06/18/2018**
- **Medical screening can be conducted by a nurse practitioner with consultation from a pediatric gastroenterologist**
- **Subjects will no longer be enrolled in our IRB #53959**

Version 3.6

- In Recruitment section, revised protocol to state that we will now be using the Oral Consent and HIPAA Authorization Script and Information Sheet for Research Study Screening instead of the Screening Protocol – IRB# 00057294

Version 3.5, drafted 01/08/2018

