Group Assignment: Participants will be randomly assigned to one of the two groups after they have it has been verified that they meet all of the eligibility criteria. Randomization to 2-week MIE or TAU will be according to a 1:1 ratio using permuted blocks stratification on constipation status. The permuted blocks will be constructed and managed by the unblinded statistician. She will receive an email form from the coordinator indicating that the participant meets all inclusion criteria and does not meet any exclusion criteria and the participant's constipation status (constipated/not constipated). This statistician will assign the subject to 2-week MIE or TAU according to the permuted block. We define constipated using the modified Rome III criteria appearing above. All other participants will be considered not constipated. Caregivers of participants randomly assigned to the MIE condition (i.e., 2 week) will be provided a handout that addresses frequently asked questions about the use of suppositories.

In the event a participant is unable to attend MIE or TAU visit(s) in the clinic after being enrolled into their assigned group, the clinician and therapists have the option to administer the intervention or TAU consultation via telehealth with the participant (e.g., WebEx, Zoom). In order to utilize telehealth, a scenario must arise that prevents the participant from being able to complete the MIE treatment or TAU consultation in the clinic. If such a scenario arises, on a case-by-case basis, then the therapist and clinician may administer via telehealth, but should return to the clinic as soon as possible to continue. Additionally, there will be one extra day added to the MIE 2-week treatment totaling 11 days instead of 10. The extra day is added to the beginning of treatment so the clinician can first explain the intervention they will be doing with the caregiver.

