Some participants may have a history of engaging in problem behaviors including, but not limited to, aggression, destructive behavior, self-injury, running away, or dropping to the floor. All members of the study team who interact with participants are trained in the Marcus Crisis Prevention Program, which consists of protective procedures in order to safely manage problem behavior. When obtaining informed consent for participation in this study, the person obtaining consent will also describe the protective procedures and emergency protocols to the family. The consent forms giving permission to use those procedures are the same as those used with clinical families. Low-intensity problem behavior will be managed within the context of the study, but more serious problem behavior will result in the study team discontinuing study procedures temporarily in order to safely manage problem behavior and may be reported to the IRB.

A total of 150 participants will be enrolled in the study and randomly assigned to one of three groups (60 in 2-week MIE, 60 in 1-week MIE, and 30 in TAU group). Starting year 3 a total of 112 participants will be enrolled in the study and randomly assigned to one of two groups (56 in 2-week MIE and 56 in TAU group). We will recruit the necessary sample over a 4-year period, with 19 participants enrolled in Year 1 to allow for ramp up, and 22 in Year 4 to leave sufficient time for participants to complete 3-months of caregiver implementation prior to follow-up and for data analysis. We will recruit 35 participants in Year 2 and 45 in Year 3.

Years	Year 1				Year 2				Year 3				Year 4			
Months	1-3	4-6	7-9	10-12	13-15	16-18	19-21	22-24	25-27	28-30	31-33	34-36	37-39	40-42	43-45	46-48
n per period	3	7	4	5	6	8	12	9	9	9	9	9	9	9	4	completion
Cumulative N	3	10	14	19	25	33	45	54	63	72	81	90	99	108	112	$\Sigma = 112$

Families will be asked to provide basic information by telephone regarding their child's difficulties via the Oral Consent and HIPAA Authorization Script and Information Sheet For Research Study Screening to determine if they meet the eligibility criteria for the study.

Training

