During the trial, the statistician will monitor missing data and errors, enrollment and attrition. When the trial is completed, descriptive statistics will be calculated for baseline data across treatment groups. Additional analyses will be undertaken to inspect data for errors, inconsistencies, and incomplete information across time points. This will include examining the data with simple frequency tables and scatter plots. Data anomalies and outliers will be examined and corrected if necessary. These preliminary analyses will include descriptive statistics in each treatment group for all outcome variables, plots of longitudinal data over time, and examination of distributions within groups at important nodal points (e.g., Baseline, weeks 2, , 4, 8, 28). All the analyses will apply the *intent-to-treat* principle. For modeling and hypothesis testing, the proposed likelihood-based approach regards missing data as missing at random (MAR; i.e, missing data are independent of unobserved data). Although there is no proven method for verifying the MAR assumption, the likelihood-based solutions are robust to violations of ignorable missing data (i.e, situations where the MAR assumption is not met).

Nevertheless, prior to analyses for efficacy, we will examine the frequency, reasons, pattern and time to dropout and missing values across treatment groups. If substantial differences in missingness occur across treatment groups that cannot be adequately explained by observed variables, secondary sensitivity analyses will be performed. These techniques will be considered cautiously in our analyses as they require certain assumptions that cannot be evaluated from the data under analysis. Statistical significance will be assessed at the 0.05 level unless otherwise noted. All analyses will be conducted using SAS v9.4 for Windows (Cary, NC, USA).

Primary outcome: A Chi-square test will be used to compare the proportion of children who achieve continence (60% of days are continent days and no more than 1

incontinent day over a 7 day period and no more than 2 incontinent days over a 14 day period) based on parent report at Week 8 (endpoint of acute randomized trial). The contrast will be MIE-2 vs TAU.

Secondary Outcome #1: A Chi-square test will be used to compare the proportion of children who are rated by the Independent Evaluator as *Much Improved* or *Very Much Improved* on the CGI-I at Week 8. The contrast will be MIE-2 vs TAU.

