Secondary Outcome #2: ANCOVA will be used to compare change in parental stress and strain from baseline to Week 8 as measured on the Parenting Stress Index and the Caregiver Strain Questionnaire. The contrast will be MIE-2 vs TAU.

Sample Size and Power Calculation for Primary Outcomes. As noted above, we will perform one planned pairwise comparison for the primary outcomes at Week 8: MIE-2 vs TAU. We set our significance level for alpha as 0.05 to control the family-wise Type I error rate at the 5% level. Based on our pilot data, we conservatively estimate the following rates of children achieving continence at Week 8: 10% of participants in TAU, 75% of those in the MIE-2 group and 50% for the MIE-1 group. With a sample size of 54 in each of the TAU MIE groups, we can detect a 29% difference in response rate on our primary categorical measure with 15% dropout rate and type I error rate of 0.05. We propose that this will be a valid test of the Two-week medical-behavioral intervention, which was, and remains, the primary aim of the study.

Data Security

Electronic Protected Health Information (ePHI) is carefully guarded within the database. All full and incremental database backups are compressed and encrypted before being sent using secure sockets layer (SSL) to a secure, geo-redundant backup infrastructure. All communication with the server for normal usage, maintenance and backups is encrypted using SSL.

The DEX database has the following Security features:

Hot Security The server runs a highly secure operating system (FreeBSD), providing immediate resistance to many common attacks and exploits. A unique web-server is used to reduce system exposure to attacks. The web server is written in a high-level language that substantially reduces the effectiveness of most common attacks (such as buffer-overflows). All communication between the site server and remote workstations (any modern computer capable of running the Firefox web browser) is logged and uses SSL encryption. The system fully supports journaling to ensure data integrity, to support audit trails, and to simplify disaster recovery. Furthermore, all collected data, as well as the journal itself, can be mirrored (in encrypted form) on redundant remote servers. In the rare case that the server is compromised, any modification to system resources can be undone by simply contacting Prometheus Research, who will restore the system from backup.

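### The primary and CGI-I chi-square tests ignore the constipation stratum and the change in MIE-2:TAU allocation, and the plan does not say whether children randomised before the change are analysed

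*Combined protocol and SAP*

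**What the plan says.** The Analytic plan gives the primary test in one line: "A Chi-square test will be used to compare the proportion of children who achieve continence". Secondary Outcome #1 follows the same form: "A Chi-square test will be used to compare the proportion of children who are rated by the Independent Evaluator as" much or very much improved. In both, "The contrast will be MIE-2 vs TAU", and no stratum, covariate or enrolment period is named. Intent-to-treat is declared for all analyses.

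Under Group Assignment: "Randomization to 2-week MIE or TAU will be according to a 1:1 ratio using permuted blocks stratification on constipation status".

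The Recruitment section still carries the three-arm design, with children "randomly assigned to one of three groups (60 in 2-week MIE, 60 in 1-week MIE, and 30 in TAU group". It then continues: "Starting year 3 a total of 112 participants will be enrolled in the study and randomly assigned to one of two groups", 56 in each. The accrual table below that text reaches 112 counting from months 1-3, not from year 3. The Version 4.1 entry in the History of Protocol Changes explains the total of 138 by saying that "112 did not include the participants that were previously enrolled into the MIE 1 week group".

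**The concern.** Two features of the randomisation are missing from the analysis, and a third matter is left open.

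- **Stratum.** Blocking within constipation status balances the arms on it. An unstratified test then overstates the variance if constipation predicts outcome. It stays valid but is somewhat conservative and loses power.
- **Allocation period.** The original targets put MIE-2:TAU at 2:1, and the current rule is 1:1. If both periods are pooled, MIE-2 holds a larger share of early children than TAU. Any change in response over time is then partly attributed to treatment: a fall favours MIE-2 and a rise favours TAU.
- **Analysis set.** The Recruitment text can be read as 112 new children from year 3. The accrual table and the Version 4.1 entry point to pooling. No sentence settles it, so the primary analysis set could be chosen after data are seen.

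**Working it through.** **The plan's own figure.** The sample-size text assumes "10% of participants in TAU, 75% of those in the MIE-2 group and 50% for the MIE-1 group" and states that 54 per group detects 29 points with 15% dropout at alpha 0.05. Power and sidedness are not given. Taking 10% v 39%, two-sided, 90% power and no continuity correction:

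n = [1.96√(2 × 0.245 × 0.755) + 1.282√(0.10 × 0.90 + 0.39 × 0.61)]² / 0.29² = 44.1, so 45 per arm; 45/0.85 = 52.9, so 53.

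This is within one of the stated 54. It is an unstratified, single-period, 1:1 calculation.

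**Implied counts if early children are pooled.**

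- MIE-1 children: 138 − 112 = 26.
- At 60:60:30, 26 in MIE-1 implies about 26 MIE-2 and 13 TAU before the change.
- Remaining: 112 − 39 = 73, which at 1:1 is about 37:36.
- Totals: 26 + 37 = 63 MIE-2 and 13 + 36 = 49 TAU, not 56:56. Reaching 56:56 would need 30:43 later, which is not 1:1.
- If all 112 were new, 112 + 26 = 138 leaves no room for any earlier MIE-2 or TAU children.

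**Bias.** Early share is 26/63 = 41.3% in MIE-2 and 13/49 = 26.5% in TAU, a gap of 14.7 points. With no treatment effect, the expected crude difference is 0.147 × (early rate − late rate): about 1.5 points per 10 points of drift.

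**Type I error** (simulation, 200,000 replicates per row, two-sided 0.05, Pearson chi-square v Cochran-Mantel-Haenszel (CMH) by period, no continuity correction; drift sizes are assumptions):

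| Early → late rate | Bias (points) | Chi-square | CMH |
|---|---|---|---|
| 10% → 10% | 0 | 5.4% | 4.8% |
| 20% → 10% | +1.5 | 5.6% | 4.9% |
| 30% → 10% | +2.9 | 6.1% | 4.9% |
| 50% → 30% | +2.9 | 5.7% | 5.1% |
| 30% → 50% | −2.9 | 5.9% | 4.9% |

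The Mantel-Haenszel risk difference has no bias in any row. With the odd child in TAU instead (36:37), a 20-point drift gives 3.2 points of bias; type I error is mostly 6.1-6.2%, reaching 7.5% for a rise from 10% to 30%. A later split of 30:43 would give +4.7 points and 7.5-9.4% for 20-point falls, but it contradicts the 1:1 rule.

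**Constipation** (56 per arm, equal strata, odds ratio 3.3, all assumed). Power, chi-square v CMH:

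| TAU rate by stratum | Chi-square | CMH |
|---|---|---|
| 15% / 8% | 68.1% | 68.0% |
| 15% / 5% | 60.8% | 61.8% |
| 20% / 5% | 64.6% | 66.7% |
| 30% / 5% | 64.8% | 70.9% |
| 60% / 20% | 74.5% | 81.0% |

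With 20%/5% and no treatment effect, type I error is 4.4% v 5.0%. At the planned 10% v 75%, power exceeds 99.9% with either test.

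**Analysis set.** At 10% v 39% after 15% loss, power is 91.6% with early children included (62.5:49.5) and 77.0% with only the later 36.5 per arm.

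**The case against.** The case for leaving the tests alone is mainly about size. The chi-square is valid without the stratum, and at the plan's own detectable difference the power gap nearly vanishes: 96.5% v 96.5% (TAU 15%/5%) and 95.2% v 95.5% (20%/5%) with 56 per arm. Gaps of 6-7 points need a strength of prognosis that no section supports. The period argument stacks assumptions: exactly 26 MIE-1 children, realised early allocation matching the 2:2:1 targets, pooling, and drift. At 10 points of drift, type I error is 5.6% against 5.4% with none, so most of the excess is discreteness of the test. The documents also lean towards pooling, so one clarifying sentence might be enough.

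Most of this stands as a limit on importance, and the point is one of robustness. It does not remove it. The direction does not depend on the assumed 26: taking the accrual table's 54 children by month 24 as 36:18 and the other 58 as 29:29 gives 1.7 points of bias per 10 of drift. Drift is not shown, but it is not fanciful. The change history records a redefined urine-continence criterion, then telehealth delivery and further diagnostic instruments added after the three-arm phase closed. That the documents lean towards pooling makes the period imbalance more relevant, since pooling is the case in which it arises.

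**Conclusion.** The concern holds. Neither binary test reflects the stratified randomisation or the change in allocation, and the primary analysis set is implied but not stated.

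If early children are pooled, bias is about 1.5 points per 10 points of drift and type I error is about 6% with a 20-point drift. This rests on 26 MIE-1 children, the 2:2:1 targets having been realised, and a drift for which there is no evidence. If the 112 are all new children, only the constipation point remains; there the test is valid and the power loss is 0-2 points unless constipation is very strongly prognostic. Against a planned 65-point difference, neither issue is likely to reverse the conclusion. The change is worth making because it is cheap and settles the analysis set in advance.

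**What to change.** 1. State whether MIE-2 and TAU children randomised under the three-arm scheme are in the primary analysis set.
2. Reconcile the 56:56 target with 1:1 allocation (about 63:49 if early children count), and the year-3 wording with the accrual table.
3. Make the primary and CGI-I tests Cochran-Mantel-Haenszel, or main-effects logistic regression, stratified by constipation status and, if early children are included, by allocation period (three-arm v two-arm). Report a Mantel-Haenszel risk difference and keep the unadjusted chi-square as a sensitivity analysis.
4. Add the same factors to the ANCOVA for the Parenting Stress Index and the Caregiver Strain Questionnaire.

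The cost is SAP wording; both factors are known at randomisation. With no drift, stratifying by both loses about 0.5-1.2 points of power: 95.9% v 95.4% at 10% v 39%, 90.1% v 89.2% at 10% v 35%, and 85.7% v 84.5% at 10% v 33%. Early TAU would be sparse (13 children, 13 × 0.10 = 1.3 expected continent), so the plan should rely on a common Mantel-Haenszel or main-effects estimate and not on stratum-specific ones.

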- 1) Evaluate the efficacy of a two-week, multidisciplinary intervention for encopresis (MIE-2) in children with ASD compared to controls receiving Treatment as Usual (TAU). We predict, based on parent report, that a significantly greater proportion of subjects in the MIE-2 group will achieve continence at endpoint (Week 8) than children in TAU.
- 2) Evaluate whether the MIE-2 group will have a significantly higher proportion of children rated *Much Improved* or *Very Much Improved* on the Improvement item of the Clinical Global Impression than children in TAU as rated by an Independent Evaluator blind to treatment assignment at Week 8.
- 3) Evaluate whether parents of children in MIE-2 will report greater reduction from baseline in parental stress and strain than parents of children in TAU at endpoint (Week 8) as measured on the Parenting Stress Index and the Caregiver Strain Questionnaire.

Procedures

This is a 28-week, randomized clinical trial of 138 (updated from 150) children, ages 5 to 12 years, 11 months with ASD and encopresis. Subjects will be randomized in a 1:1 ratio to receive either two weeks of MIE or one week of Treatment as Usual (TAU). See Figure 1 for an outline of study procedures described below.

As shown in the Figure, Week 8 is an important nodal point in the study. At Week 8, participants will be classified as having achieved continence or not. This classification at Week 8 is the primary outcome for the study.

[figure not shown]

Figure 1

Screening: Prior to enrollment all potential participants will be evaluated for study eligibility through an initial phone screen. At the beginning of this screening, we will provide the family with a short study synopsis. We will then complete the Oral Consent and HIPAA Authorization Script and Information Sheet for Research Study Screening. This is a verbal consent form that gives us permission to collect and store protected health information over the phone. This form will be read to the families to ensure they understand the information we are collecting and their rights as a research subject. This screening will consist of gathering information on the participants' age, parent reported diagnosis, and problem behavior. Participants will be excluded if their caregiver does not report that the child meets the age or diagnostic criteria. If the caregiver indicates that the child engages in problem behavior, additional information

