will be gathered to determine if problem behavior is likely to interfere with the treatment protocol. If problem behavior is deemed likely to interfere they will be excluded from participation. Caregivers will also be asked to keep a log of the frequency of their child's continent and incontinent bowel movements from the day of the phone screen until the characterization appointment to further confirm study eligibility.

Characterization, the Medical Assessment, and collection of Baseline Measures will take place across either 1 or 2 days, depending on participant and clinician availability, as well as the ability of the participant to tolerate lengthy assessments. Although the medical screening may precede characterization if scheduling requires, characterization will take place first whenever possible because participants are thought to be more likely to meet diagnostic exclusionary criteria than medical exclusionary criteria.

Consenting: A member of the research team will obtain informed consent from the caregiver(s) of each participant prior to completing any study procedures. We will not obtain assent from participants because it is anticipated that most will not possess the cognitive capacity to give assent and because refusal to comply with toileting routines is the condition that is being targeted for intervention. At this meeting caregivers will be asked to keep concomitant medications stable and to notify us if this is not the case during the study. Caregivers of participants will be provided a handout that addresses frequently asked questions about the use of suppositories.

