Baseline Phase (Weeks 1-2): All participants' caregivers, regardless of group assignment will implement any medical recommendations for constipation throughout a Baseline Phase. In addition, all caregivers will collect data on their child's bowel movements during Baseline. It is anticipated that this phase will last for 14 days, but due to scheduling issues it may last for 12 to 21 days. Data collection will include frequency of continent and incontinent bowel movements and whether any medication (i.e., a suppository) was used prior to the bowel movement on data sheets provided by the research team. Caregivers will be asked to enter data from the datasheets electronically directly into our project database via a unique and secure login provided during the characterization visit. Caregivers who do not enter data for a given day will receive a reminder email the next day. A research coordinator will also call caregivers who are missing data on a weekly basis to see if they entered it on the datasheet but did

not enter it electronically. In cases in which the family does not have access to the internet, the data will be collected over the phone. Caregivers will be asked to bring the data sheets to their first visit in the clinic.

Baseline Visit: Baseline data will be collected on the first day of MIE or TAU, before the appointment occurs. A member of the research team will meet with caregivers to complete the remaining baseline measures. The following measures will be completed: Parent Target Problem (PTP), Parenting Stress Index-Short Form (PSI-SF), Aberrant Behavior Checklist (ABC) Clinician Global Impression-Severity (CGI-S), Caregiver Strain Questionnaire-Short Form (CGSQ-SF), Adverse Event, Safety Review, Concomitant Medication Log .

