2. DSM-5 diagnosis of *Autism Spectrum Disorder* as established by clinical assessment, corroborated by the Autism Diagnostic Observational Schedule, Autism Diagnostic Interview-Revised and/or Childhood Autism Rating Scale-Second Edition.
3. Fewer than 60% of days are continent days or more than 1 day out of 7 is an incontinent day over the previous 7 days (a continent day is defined as a day with at least one continent bowel movement. An incontinent day is a day with an incontinent bowel movement regardless of whether a continent bowel movement also occurs).
4. Medication free or on stable medication (no changes in past 6 weeks and no **planned** changes for the next 6 months) [RATIONALE: Inclusion of children on stable medication

eliminates a potential confounding variable and enhances the generalizability of study findings].

5. Urine continent – Over half of the voids are continent when the child is with the parent and when the child is on a typical toileting routine.

Exclusion Criteria

1. Presence of a known medical condition in the child (based on medical history or physical examination by a gastroenterologist or nurse practitioner working in consultation with a gastroenterologist) that would interfere with child's ability to control his/her anus. These include:

- History of any anal surgery
- Spinal dysraphism (e.g., spina bifida)
- Other neurologic disorder affecting anal function
- Prolonged/recurrent gastrointestinal infectious disease (e.g. Clostridium difficile colitis)

In addition, the following may constitute exclusions following evaluation by a physician:

- Inflammatory bowel disease
- Short gut syndrome
- Chronic diarrhea
- History of intestinal/abdominal surgery

[RATIONALE: inability to control the anus is highly likely to prevent the success of any treatment for encopresis. All medical conditions will be reviewed by study team to make a final determination of eligibility.]

2. Presence of a current serious behavioral problem or psychiatric condition that would require another treatment (e.g., psychotic disorder, major depression, moderate or greater aggression, severe disruptive behavior), based on information collected at screening and the Behavior Problems Inventory-01 (BPI-01; as described below). [RATIONALE: presence of an untreated serious behavioral problem or psychiatric condition would interfere with the child's ability to participate in the treatment.]

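### The primary chi-square is valid but uses neither the pre-randomisation bowel log nor the stratification factor, so it gives up some precision and leaves chance imbalance in baseline severity uncorrected

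*Combined protocol and SAP*

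**What the plan says.** - **Primary test.** Analytic plan, Primary outcome: "A Chi-square test will be used to compare the proportion of children who achieve continence" at Week 8, MIE-2 v TAU. No covariate, stratum or adjusted sensitivity analysis is named. The likelihood-based approach described earlier in that section deals with missing data and sets out no model for this endpoint.
- **Pre-randomisation log.** Procedures, Screening: caregivers log "continent and incontinent bowel movements from the day of the phone screen until the characterization appointment", to help confirm eligibility.
- **Entry range.** Inclusion criterion 3: "Fewer than 60% of days are continent days or more than 1 day out of 7 is an incontinent day", judged over the previous 7 days. An incontinent day counts as such even if a continent movement also occurred that day.
- **Timing and stratification.** Group Assignment: children are randomised "after they have it has been verified that they meet all of the eligibility criteria", "using permuted blocks stratification on constipation status".
- **Later diary.** Baseline Phase: caregivers "regardless of group assignment will implement any medical recommendations for constipation throughout a Baseline Phase" and keep a further diary for 12 to 21 days. As described, this follows assignment.
- **Other outcomes.** Chi-square is also planned for CGI-I response, and ANCOVA for parental stress and strain.

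**The concern.** Criterion 3 admits a wide range of severity. A child with no continent movement at all qualifies. So does a child with 6 continent and 2 incontinent days in 7, because the two kinds of day can overlap. That second child is one incontinent day short of the 7-day endpoint rule. How far a child is from the threshold at entry may well predict whether the child crosses it by Week 8.

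Stratifying on constipation status balances that factor, but not the frequency of soiling. If one arm happens to receive more near-threshold children, the unadjusted difference absorbs the imbalance. The plan describes baseline data by arm only when the trial is completed. An adjustment adopted after an imbalance has been seen would be post hoc and open to challenge. Stratification on constipation can also improve precision if the factor is prognostic, and an analysis that omits it does not credit that gain.

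**Working it through.** **Inputs.** From Sample Size and Power Calculation: 54 per arm, 15% dropout, alpha 0.05, 10% continent in TAU, 75% in MIE-2, detectable difference 29 points. Power and sidedness are not stated; I assume a two-sided test. Evaluable per arm: 54 x 0.85 = 45.9, about 46. The prognostic strength of the log is not in the documents, so a range is assumed.

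**Step 1: reproduce the 29 points.** Take TAU at 10%, so MIE-2 at 39% and the mean proportion 0.245.

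n = [1.960 x sqrt(2 x 0.245 x 0.755) + 1.282 x sqrt(0.10 x 0.90 + 0.39 x 0.61)]^2 / 0.29^2 = (1.192 + 0.734)^2 / 0.0841 = 44.1, so 45 per arm.

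45 / 0.85 = 52.9, so 53, against the stated 54. The figure is reproduced at 90% power. With 46 per arm, power = Phi[(0.29 x sqrt(46) - 1.192) / 0.573] = Phi(1.35) = 91.2%. The reading is not unique: 35.5% v 64.5% at 80% power gives 55 per arm.

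**Step 2: effect of adjustment at 10% v 39%.** Simulation with 46 per arm and 4,000 trials per setting, comparing the crude difference with a logistic model on one baseline covariate, standardised to a risk difference. The slope is the log-odds per SD of the covariate.

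| Slope | Variance, crude/adjusted | Adjusted/crude (reciprocal) | Power, adjusted |
|---|---|---|---|
| 0 | 0.99 | 1.01 | 92% |
| 0.5 | 1.02 | 0.98 | 93% |
| 1.0 | 1.13 | 0.88 | 96% |
| 1.5 | 1.27 | 0.79 | 97% |

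Unadjusted power in these runs is 92-93%. With the stratum added to the model, and over the event rates examined, the adjusted/crude variance ratio is 1.00-1.02 at slope 0 and 0.75-0.98 at slopes 0.5-1.5. That is the source of +2% to -25%.

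**Step 3: analytic check.** If the covariate explains a share R2 of outcome variance, effective n is 46 / (1 - R2). At R2 = 0.20 this is 46 / 0.80 = 57.5. Power at 10% v 39% rises from 91.2% to 96.1%, and the difference detectable with 90% power falls from 28.3 to 24.8 points.

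**Step 4: the planned 10% v 75%.** Power exceeds 99.9% with or without adjustment. The standard error falls from about 0.079 to 0.071 at slope 1.5; (0.0714 / 0.0794)^2 = 0.81.

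**Step 5: chance imbalance.** The SE of a difference in covariate means is sqrt(2/46) = 0.209 SD. An imbalance above 0.3 SD is 0.3 / 0.209 = 1.44 SEs, so it occurs in about 15% of trials in either direction. Given such an imbalance at 10% v 39%, the crude difference moves on average by about 2, 6 and 7 points for slopes 0.5, 1.0 and 1.5. The adjusted estimate stays within about 1 point.

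**Step 6: Type I error.** In null simulations the unadjusted test rejected 4.5-6.6% of the time and the one-covariate adjusted analysis 4.9-6.3%.

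**The case against.** The case for leaving the chi-square alone is substantial, and several parts of it stand.

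- **It is not an error.** A reader might infer that the chi-square is biased or invalid. It is neither: randomisation protects it, and its null rejection rate is close to that of the adjusted analysis.
- **The ANCOVA is not an inconsistency.** The plan uses chi-square for both binary outcomes and ANCOVA for the continuous ones. That is a common pattern, not a contradiction.
- **Power is not at risk on the plan's own rates.** A reader might infer that adjustment lifts power from about 80% to 90%. That needs a control rate near 35.5%, which the plan does not state. From its own 10% TAU rate, power at a 29-point difference is already about 92%.
- **The log may predict weakly.** Every child is non-continent at entry, so the range is restricted. Constipation treatment normally starts after the log ends and could change the pattern recorded.
- **The change is not free.** The screening log appears in neither Table 1.0 nor Table 2.0 and has no stated minimum length. The 7-day minimum under Visit Windows, and the data-entry and reminder procedures, belong to the later diary.
- **Too many covariates would erode the gain.** With two related log proportions (assumed correlation -0.7, the second adding nothing), the variance ratio at 10% v 39% is 1.02, 0.99, 0.94 and 0.85 for slopes 0, 0.5, 0.8 and 1.2.

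Against this, criterion 3 cannot be verified without day-level status over 7 days, so one usable baseline value should exist for each eligible child. If that value proves not to be prognostic, the cost in variance is at most about 2%. An imbalance shift of 2 to 7 points is small beside a planned 65-point effect (75 - 10), but less so beside the 29 points the plan also quotes.

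**Conclusion.** The point holds as one of efficiency and robustness. The primary analysis leaves out a baseline measure in the same domain as the outcome, and also the stratification factor. Over assumed slopes of 0 to 1.5 per SD with 46 per arm, adjusting changes the variance of the risk difference by about +2% to -25%. Power at 10% v 39% goes from about 92% to 93-97% at slopes of 0.5 and above. At the planned 10% v 75% power is about 100% either way, so the gain there is a narrower interval and protection from imbalance.

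These figures rest on a two-sided 0.05 test, the plan's 15% dropout and an undocumented prognostic strength. The documents do not support calling the planned test wrong or the trial underpowered for this reason. Pre-specified adjustment is worth making, at modest priority.

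**What to change.** Pre-specify as primary a logistic regression of Week 8 continence on arm, constipation status and one log summary: the proportion of incontinent days over the 7 days used to confirm criterion 3. One summary is enough. At 10% v 39%, 46 x (0.10 + 0.39) = 22.5, so only about 23 events are expected.

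- Name the single test of the arm term that decides the result, and its sidedness.
- Report the standardised risk difference with 95% CI.
- Keep the unadjusted chi-square as a supportive analysis.
- Do not use the Baseline Phase diary as the covariate. As described it is kept after assignment, by caregivers who may know the group.
- State a penalised fit to be used if there is separation.

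**Cost.** A change to the analysis text, plus entry of the screening log in the study database and a stated rule for short or missing logs (mean fill or a missing indicator). No new assessment of the child is needed.
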